## 8.5 Procedures

Prior procedures, procedures maintained during the randomized treatment period and concomitant procedures will be summarized by treatment group for the Safety Set through frequency distributions and percentages by SOC and PT. Post-treatment procedures will only be presented in a listing.

The procedures will be classified according to the following rules (See also Section 7.3):

- Prior procedure: start date/time < date/time of first randomized study medication intake and stop date  $\leq$  date/time of first randomized study medication intake;
- Procedure maintained during the randomized treatment period: start date/time < date/time of first randomized study medication intake and stop date/time > date/time of first randomized study medication intake or ongoing;
- Concomitant procedure: date/time of first randomized study medication intake  $\leq$  start date/time < date/time of last randomized study medication intake;
- Post-treatment procedure: date/time of last randomized study medication intake  $\leq$  start date/time.

## 8.6 Compliance

No treatment compliance will be derived.

## 9 Efficacy Analyses

All the efficacy comparisons between the treatment arms including the primary will be based on the FAS and the ITT Set will be used for sensitivity analysis for the primary efficacy analysis. The PP Set will be used for sensitivity analysis for the primary efficacy analysis and also as the primary analysis for the non-inferiority analyses.

## 9.1 Primary Efficacy Variable

The primary efficacy variable is the percentage of subjects who have treatment success following a single instillation of study drug (CUSA-081, alteplase, or placebo) with a dwell time up to 90 minutes. Treatment success will be derived as mentioned in Section 7.3.

Protocol violations and any other intercurrent events will be ignored for analyses performed on the FAS, which target a treatment policy estimand. Subjects with important protocol deviations will be excluded from analyses based on the PPS.

### Superiority Hypotheses

The hypothesis corresponding to the primary efficacy analysis is as follows:

The null hypothesis H0:  $R_c - R_p = 0$   
The alternative hypothesis H1:  $R_c - R_p > 0$

Where  $R_c$  = Rate of success of CUSA-081  
 $R_p$  = Rate of success of placebo

Additional hypotheses are constructed in a similar manner for secondary study objectives to demonstrate superiority.

The number of subjects will be presented by treatment group. The percentage of subjects with treatment success and two-sided 95% Wald CI will be presented by treatment group. Treatment effects will also be presented as the mean difference in proportions (CUSA-081 versus placebo or alteplase) together with the 95% Wald CI and p-value based on a 2-sample Z test for proportions.

Superiority of CUSA-081 over placebo or alteplase will be demonstrated by a statistically significant difference (p-value < 0.05) between treatments with a dwell time up to 90 minutes favoring CUSA-081 using a 2-sample Z test for proportions.

A two-sided 95% confidence interval on the difference in rates of restoration of CVAD function between treatment groups will be constructed from SAS Proc Freq, option Riskdiff for treatment difference (See Section 14.1).

A sensitivity analysis will also be performed as a test of the superiority of alteplase versus placebo in the rate of treatment success following a single administration of study drug with a dwell time up to 90 minutes. This sensitivity analysis will be performed at the same time as the non-inferiority assessment, using the same statistical methodology as for the other analyses of superiority, without adjustment for multiplicity.

### Non-Inferiority Hypotheses

The hypotheses for the non-inferiority are as follows:

The null hypothesis H0:  $R_c - R_a \leq -10$   
The alternative hypothesis H1:  $R_c - R_a > -10$

Where Rc=Rate of success of CUSA-081  
Ra=Rate of success of alteplase

Assessment of non-inferiority will be based on the 95% confidence interval for the difference in the rate of treatment success between CUSA-081 vs alteplase following a single administration with a dwell time up to 90 minutes.

Non-inferiority will be demonstrated (or null hypothesis will be rejected) when the lower limit of the 95% confidence interval for the difference in rate of success is greater than -10% (See Section 14.1).

The number and percent of subjects with treatment success by treatment group and time point will be summarized. The rate difference and associated 95% Wald confidence intervals between CUSA-081 and placebo or alteplase will be estimated. The between treatment comparisons will be performed using a 2-sample z test for proportions.

For superiority hypotheses, the primary analysis will be the analysis performed on the FAS. Analyses will be repeated based on the ITT and PP Sets as sensitivity analyses. For non-inferiority hypotheses, the analysis based on the PP Set will be considered as the primary analysis.

### **Sensitivity Analysis**

A sensitivity analysis will be performed on the primary efficacy endpoint using a logistic regression model with age (<18, ≥18-<65, ≥65-<85, ≥85 years) and region (US vs Non-US) as factors. The odds-ratio, 95% confidence interval for the odds-ratio and the p-value will be displayed for each treatment group comparison (See Section 14.4).

## **9.2 Secondary Efficacy Variables**

All the below efficacy endpoints will be analyzed based on FAS, ITT and PP Set.

### **9.2.1 Percentage of Subjects Who Have Treatment Success Following a Single Instillation of Study Drug with a Total Dwell Time Up To 30 and 60 Minutes**

The rate of treatment success following a single administration with a dwell time up to 30 and 60 minutes will be analyzed using the same method as the primary efficacy variable.

### **9.2.2 Percentage of Subjects Who Have Treatment Success After Up to Two Instillations of Study Drug with a Total Dwell Time Up To 120, 150 and 180 Minutes**

The rate of treatment success following up to two administrations with a dwell time up to 120, 150 and 180 minutes will be analyzed using the same method as the primary efficacy variable.

## **9.3 Other Secondary Efficacy Variables**

### **9.3.1 Rate of Recurrent Catheter Dysfunction Within 30 Days Following Treatment with Study Drug**

The rate of recurrent catheter dysfunction defined as first re-occlusion within 30 days following treatment (CUSA-081, placebo or alteplase) will be displayed by treatment group.

Time to first re-occlusion will be derived only for subjects with treatment success as follows:

- Time to first re-occlusion (days) = (date of start of first re-occlusion – date of first treatment success assessment date + 1), if subject has a re-occlusion.
- Time to first re-occlusion (days) = (date of CVAD – first treatment success assessment date + 1), if the subject removed the CVAD before end of study (censored).
- Time to first re-occlusion (days) = (date of study completion/discontinuation – first treatment success assessment date + 1), if the subject is censored (i.e. no re-occlusion before end of study and no CVAD removal).

The time to first re-occlusion will be analyzed using the Kaplan-Meier method with median, 25th and 75th percentiles and 95% CI (See Section 14.2). The estimated probability of re-occlusion free at day 30 and its 95% CI will be presented by treatment group. A Kaplan-Meier plot will also be presented.

In addition, time to first re-occlusion will be analyzed using a Cox proportional hazards model including treatment as factor. Treatment effects will be presented as a hazard ratio with the associated 95% Wald CI (See Section 14.3).

These analyses will be based on all subjects with treatment success following up to two administrations of study drug with a total dwell time up to 180 minutes within FAS.

Additional efficacy analyses including demographics and baseline characteristics as covariate/subgroup may be explored, if needed.

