12.3.5 Secondary Efficacy Variables

The number and percent of subjects with treatment success by treatment and time point will be summarized. The rate difference and associated 95% Wald confidence intervals between CUSA-081 vs. placebo and alteplase will be estimated. The between treatment comparisons will be performed using a 2-sample z test.

The rate of recurrent catheter dysfunction defined as first re-occlusion within 30 days following treatment will be analyzed using the Kaplan-Meier method and summarized with median, 25th and 75th percentiles, and 95% confidence intervals. The rate of recurrent catheter dysfunction will be estimated. This analysis will be based on all subjects with treatment success following up to two administrations of study drug with a total dwell time up to 180 minutes.

Additional efficacy analyses including demographics and baseline characteristics as covariate/subgroup may be explored.

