Table 14.2.2.5.3	Summary and Sensitivity Analysis of Proportion of Subjects with Treatment Success Up to 180 Minutes Following Two Instillations of Study Drug - Logistic Regression Model (Per-Protocol Set)	ANT004	Same as Table 14.2.2.5.1	Same as Table 14.2.2.5.1

Table Number	Table Title	Template Code	Notes	Footnotes/Source Listing Number
Table 14.2.3.1	Rate of Recurrent Catheter Dysfunction Within 30 Days (Full Analysis Set)	TPT005	
Parameters to display:
 
 
- Number (%) of Subjects with Treatment Success [2]
 
- Number (%) of Subjects with Re-Occlusion [3]
 
- Number (%) of Censored Subjects [3]
 
- Time to Re-Occlusion (Days):               
 
- 25th Percentile (95% CI)
 
- Median (95% CI)
 
- 75th Percentile (95% CI)
 
 
 
- Probability of Re-Occlusion Free at Day 30 (95% CI)
 
- Treatment Comparison vs Placebo [4]               
 
- Hazard Ratio (95% CI) [to be displayed in CUSA-081 and Alteplase columns]
 
 
 
- Treatment Comparison vs Alteplase [4]               
 
- Hazard Ratio (95% CI) [to be displayed in CUSA-081 column]
 
 
 
	
Source: Listing 16.2.6.4
 
Footnotes:
 
[1] Time to re-occlusion (Days) = (date of start of first re-occlusion – date of first treatment success + 1). If no re-occlusion the subject is censored to the CVAD removal or study discontinuation/completion date, whichever is the earliest.
 
[2] Percentages are based on the number of subjects in the FAS.
 
[3] Percentages are based on the number with treatment success.
 
[4] Based on Cox proportional hazards model including treatment as a fixed effect.

Table 14.2.3.2 ***	SAS Output: Rate of Recurrent Catheter Dysfunction Within 30 Days (Full Analysis Set)		Raw SAS output	

Table Number	Table Title	Template Code	Notes	Footnotes/Source Listing Number

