Listing 16.2.6.2	Central Venous Access Device at End of Treatment (Intention-to-Treat Set)		Variables to be listed: 
 
- Subject ID
 
- Randomized Treatment
 
- Actual Treatment
 
- Patency Achieved Within 180 Minutes? Assessment
 
- If No               
 
- What Standard of Care Treatment Was Applied?
 
- Date/Time of Treatment
 
- Outcome
 
 
 
	
Listing 16.2.6.3	Central Venous Access Device Follow-up (Intention-to-Treat Set)		Variables to be listed: 
 
- Subject ID
 
- Randomized Treatment
 
- Actual Treatment
 
- Achieving Patency During the 180-minute Treatment Period?
 
- Re-Occlusion Since the Treatment Visit?
 
- Date of First Re-Occlusion
 
- Date of Additional Treatment for CVAD Dysfunction
 
- Type of Treatment
 
- Study Treatment CVAD Removed?
 
- Date of CVAD Removal?
 
	

Listing Number	Listing Title	Template Code	Notes	Footnotes
Listing 16.2.6.4	Central Venous Access Device – Time to First Re-Occlusion (Intention-to-Treat Set; Subjects Achieving Patency During the 180-minute Treatment Period)		Variables to be listed: 
 
- Subject ID
 
- Randomized Treatment
 
- Actual Treatment
 
- Date/Time of First Study Drug Administration [Day]
 
- Date/Time of Treatment Success [Day]
 
- Date of First Re-Occlusion [Day]
 
- Date of CVAD Removal [Day]
 
- Date of Study Completion/Discontinuation [Day]
 
- Time to First Re-Occlusion (Days)*
 
	Footnotes: [1] * Censored. [2] Time to re-occlusion (Days) = (date of start of first re-occlusion – date of first treatment success + 1). If no re-occlusion the subject is censored to the CVAD removal or study discontinuation/completion date, whichever is the earliest. The time to first re-occlusion is derived only for subjects who have treatment success.

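### The Day 30 re-occlusion estimate censors catheter removal: the SAP should say which 30-day rate it means and add a cumulative incidence with a confidence interval

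*SAP*

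**What the plan says.** The sixth secondary objective (Protocol 2.2, SAP 3.2) is the rate of first re-occlusion within 30 days. Protocol 12.3.5 says that this rate "will be analyzed using the Kaplan-Meier method and summarized with median, 25th and 75th percentiles, and 95% confidence intervals".

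SAP 9.3.1 restricts the analysis to treatment successes in the FAS and repeats the method: "The time to first re-occlusion will be analyzed using the Kaplan-Meier method with median, 25th and 75th percentiles and 95% CI". The Day 30 summary is stated as follows: "The estimated probability of re-occlusion free at day 30 and its 95% CI will be presented by treatment group". Removal ends follow-up as a censoring event: time runs only to the removal date "if the subject removed the CVAD before end of study (censored"). A footnote to Table 14.2.3.1 gives the order of precedence: "If no re-occlusion the subject is censored to the CVAD removal or study discontinuation/completion date, whichever is the earliest". A re-occlusion therefore counts as an event even if the catheter is removed later. The code in SAP 14.2 has one event type and one censoring code. Death is not named in SAP 9.3.1. A death would apparently be censored at study discontinuation.

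Table 14.2.3.1 also has a crude row, "Number (%) of Subjects with Re-Occlusion [3"], whose footnote reads "Percentages are based on the number with treatment success". It reports the number censored and a Cox hazard ratio as well. Listing 16.2.6.3 shows whether and when re-occlusion occurred, whether and when the catheter was removed, the type of any further treatment, and "Date of Additional Treatment for CVAD Dysfunction". It shows no reason for removal.

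**The concern.** Removal is a competing event: after it, re-occlusion of that catheter is impossible. Censoring it treats the subject as someone who could still re-occlude and simply was not watched. The resulting Day 30 figure answers what would happen if every catheter stayed in place, and only if removal is unrelated to re-occlusion risk. The objective can equally be read as the share of successes who re-occlude within 30 days. The SAP does not say which is meant, and the only Day 30 estimate with a confidence interval is the first kind.

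Independence of removal is also open to question. Protocol 1.1 says that occluded catheters often have to be replaced. Footnote 9 to the study schedule collects further thrombolytic use and catheter removal or replacement under the assessment of recurrent dysfunction. The SAP uses the removal date only to censor and does not use the re-treatment date. A success re-treated or removed for dysfunction, with no re-occlusion recorded, would stay a non-event. At stake is how the 30-day rate is read in the study report.

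**Working it through.** The documents give no re-occlusion rate, removal rate or event count for this endpoint, so there is no planned figure to reproduce. The rates below are assumptions chosen to show size.

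**1. Gap between 1-KM and cumulative incidence.** Let a be 1-KM at Day 30 and r the net probability of removal by Day 30, with constant hazards:

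- h = -ln(1 - a)
- g = -ln(1 - r)
- cumulative incidence = h/(h + g) × [1 - exp(-(h + g))]

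For a = 20%, h = 0.2231:

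| r | g | h/(h+g) | 1 - exp(-(h+g)) | Cumulative incidence |
|---|---|---|---|---|
| 10% | 0.1054 | 0.679 | 0.28 | 19.0% |
| 20% | 0.2231 | 0.500 | 0.36 | 18.0% |
| 40% | 0.5108 | 0.304 | 0.52 | 15.8% |

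For a = 30% the same removal shares give 28.6%, 27.1% and 23.8%. Over a grid of a from 5% to 30% and r from 5% to 50%, the excess runs from 0.1 to 7.9 percentage points. It is zero if no catheter is removed.

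**2. Timing of removals.** Take 300 successes, one re-occlusion per day for 30 days (crude 30/300 = 10.0%) and 60 removals. Then 1-KM is 11.2% with removals spread evenly, 12.3% if all fall on days 1 to 5, 10.2% if all fall on days 26 to 30, and 10.0% with none. The excess depends on removals that precede later re-occlusions.

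**3. Bias in the other direction.** Suppose a share f of the censored removals were in fact failures with no re-occlusion recorded. True failure is then the cumulative incidence plus f times the proportion removed first.

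- a = 20%, r = 20%: cumulative incidence 18.0%, removed first 18.0%. Break-even f = (20.0 - 18.0)/18.0 = 11%. With f = 100%, true failure is 36.0%.
- a = 10%, r = 20%: cumulative incidence 8.98%, removed first 19.02%. Break-even f = (10.00 - 8.98)/19.02 = 5.4%. With f = 25%, true failure is 8.98 + 0.25 × 19.02 = 13.7%, against a 1-KM of 10.0%.

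A small share of unrecorded failures therefore reverses the sign.

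**4. The crude percentage.** It equals the cumulative incidence when every success is followed to re-occlusion, removal, death or Day 30. Otherwise it counts subjects lost early as non-events. It is also not cut at Day 30, although the follow-up visit may fall two days either side.

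**The case against.** The strongest reply is that the simple proportion is already planned. Table 14.2.3.1 gives the number and percentage with re-occlusion over all successes, next to the number censored. With complete follow-up that is the cumulative incidence. This stands, and it means objective 6 does not rest on Kaplan-Meier alone. What is missing is a confidence interval and any allowance for loss to follow-up.

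Second, a reader might infer that removal differences between arms would appear as re-occlusion differences in the planned analysis. The documents do not support this. If two arms share the same re-occlusion hazard (1-KM 20%) and have non-informative removal of 10% and 40%, Kaplan-Meier shows 20% in both and the Cox hazard ratio is unaffected. The cumulative incidence shows 19.0% and 15.8%, a 3.2-point difference produced by removal alone. The planned analysis would mislead in this way only if removal were informative, which is plausible but not shown.

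Third, a reader might infer that the censoring rule hides catheters that failed and were then removed. It does not when the re-occlusion is reported: re-occlusion is asked about directly, subjects are told at discharge to record its date (Protocol 7.1.1), and a reported one takes precedence over removal. Only unreported failures are missed.

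Fourth, the collected data limit the remedy. SAP 7.12 says that all eCRF data are listed, and no reason for removal appears, so removals for dysfunction cannot be separated without going to source. Further treatment may also concern another lumen, which Protocol 3 restricts only during the 180-minute treatment period. Counting every such treatment as re-occlusion could create false events.

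Finally, the gap may be small beside sampling error. With an assumed 300 successes and a 20% rate, the 95% half-width is 1.96 × √(0.2 × 0.8/300) = 4.5 points, against 1 to 2 points at 10% to 20% removal.

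**Conclusion.** The point holds as a gap in specification. The Day 30 estimate that carries a confidence interval is a catheter-in-place risk, the SAP does not say that this is the intended rate, and no competing-risk estimate is planned. For recorded re-occlusions, 1-KM exceeds the cumulative incidence when removals precede later re-occlusions, by 1.0, 2.0 or 4.2 points at a 1-KM of 20% with 10%, 20% or 40% removal. Those figures rest on constant hazards and assumed removal shares.

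It is tempting to say that Kaplan-Meier overstates the true failure rate. The documents do not support that, because unrecorded failures pull the other way and neither their share nor the removal rate is known. Kaplan-Meier and Cox with removal censored remain legitimate for the catheter-in-place and cause-specific questions.

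The impact is modest. Objective 6 is to be evaluated, not tested, and stands outside the hierarchy of the primary objective and secondary objectives 1 to 4 (SAP 7.2.1).

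**What to change.** 1. State in SAP 9.3.1 which 30-day rate is meant: the share of successes who re-occlude, or the risk while the catheter is in place.
2. Add to Table 14.2.3.1 the Day 30 Aalen-Johansen cumulative incidence with 95% CI by arm (PROC LIFETEST with EVENTCODE). Removal without prior re-occlusion, and death, are the competing events. This needs a status variable with separate event codes in place of the present two-level indicator.
3. Keep the Kaplan-Meier curve and the Cox hazard ratio, labelled as the catheter-in-place and cause-specific analyses.
4. Add a sensitivity analysis with two parts. The first counts further treatment for dysfunction of the study lumen as re-occlusion on its recorded date; the lumen is not in the listing and would have to be confirmed at the blind data review. The second, as a worst case, counts every removal without a recorded re-occlusion as a failure, because no reason for removal is listed.

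The cost is SAP wording and a little programming. The main cumulative incidence uses the removal and disposition data already collected, while lumen or reason for removal may need source queries. The downside is a second rate to explain, one that also depends on each arm's removal rate and so should not be read alone as a comparison of re-occlusion risk.

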### 3.2 Secondary Objectives

1. To demonstrate the non-inferiority of CUSA-081 compared to alteplase in the rate of treatment success following a single administration with a dwell time up to 90 minutes;
2. To demonstrate the superiority of CUSA-081 compared to placebo in the rate of treatment success following a single administration with a dwell time up to 60 minutes;
3. To demonstrate the superiority of CUSA-081 compared to placebo in the rate of treatment success following up to two administrations with a dwell time up to 180 minutes;
4. To demonstrate the superiority of CUSA-081 compared to alteplase in the rate of treatment success following a single administration with a dwell time up to 90 minutes;
5. To evaluate the safety and tolerability of CUSA-081;
6. To evaluate the rate of recurrent catheter dysfunction defined as first re-occlusion within 30 days following treatment with CUSA-081.

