## 5 Sample Size

For the primary assessment of the superiority of CUSA-081 vs. placebo, a sample size of 450 in the active arm (CUSA-081), and 50 in the control arm (placebo), will provide >99% power to detect a difference of  $\geq 35\%$  using a two-sided test at significance level of 0.05. The expected placebo response rate is approximately 20%.

For the assessment of the non-inferiority of CUSA-081 vs alteplase, a sample size of 450 in the active arm (CUSA-081), and 300 in the control arm (alteplase) will provide 87% power at the 2.5% significance level (that is by using one-sided 97.5% confidence intervals (CI)) with a non-inferiority margin of -10%, assuming an equal response rate of 75% in the control arm (alteplase), and the active (CUSA-081) arm. A sample size of 450 in the active arm (CUSA-081), and 300 in the control arm (alteplase) will also provide 92% power to detect a difference of 10% between the success rates using a two-sided test at significance level of 0.05.

A minimum of 841 subjects will be randomized in order to achieve a minimum of 800 subjects completing the study.

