## 12 Changes in the Planned Analyses from Study Protocol

- The protocol Section 12.2 describes the FAS as “the primary analysis set for all efficacy analyses”. The first secondary objective is “to demonstrate the non-inferiority of CUSA-081 compared to alteplase in the rate of treatment success following a single administration with a dwell time up to 90 minutes”. The primary analysis corresponding to this objective, which is included within the hierarchical closed testing procedure, will be based on the Per-Protocol Set, since this approach is considered as more conservative as per Section 5.2.3 of ICH E9. The FAS will be the primary analysis set for all efficacy analyses involving assessment of superiority.
- The protocol Section 12.3.7 describes an interim futility analysis. Since the study has been terminated by the Sponsor prematurely for other reasons, the futility analysis will not be conducted. The analysis to be conducted following the premature closure of the study will be exactly the analysis which is planned for end of study. The database lock and unblinding will be conducted according to the relevant SOPs of the Sponsor and CRO and the analysis conducted will be considered as the final study analysis.
- The definition of the Per-Protocol Set has been modified to use Safety Set instead of ITT Set in order to include in the Per-Protocol Set only treated subjects.

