### 14.3 Cox Proportional Hazards Model

```
PROC PHREG data=<dataset>;  
    CLASS trt01pn / param=glm order=internal;  
    MODEL time*censor(1) = trt01pn;  
  
    CONTRAST 'CUSA-081 vs Placebo'    trt01pn 1 -1 0 / estimate=exp e;  
    CONTRAST 'CUSA-081 vs Alteplase'   trt01pn 1 0 -1 / estimate=exp e;  
    CONTRAST 'Alteplase vs Placebo'    trt01pn 0 -1 1 / estimate=exp e;  
RUN;
```

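### SAP 9.3.1 labels responder-only re-occlusion hazard ratios as treatment effects; the two against placebo are the least protected by randomisation and would rest on very few events

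*SAP*

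**What the plan says.** The sixth secondary objective is "To evaluate the rate of recurrent catheter dysfunction defined as first re-occlusion within 30 days following treatment with CUSA-081" (SAP 3.2). Protocol 12.3.5 says that this rate "will be analyzed using the Kaplan-Meier method and summarized with median, 25th and 75th percentiles, and 95% confidence intervals", restricted to subjects with success by 180 minutes. It names no regression model and no hazard ratio.

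SAP 9.3.1 keeps the Kaplan-Meier analysis and adds a Cox model with treatment as the only factor: "Treatment effects will be presented as a hazard ratio with the associated 95% Wald CI". The next sentence gives the analysis set: "These analyses will be based on all subjects with treatment success following up to two administrations of study drug", within the FAS and up to 180 minutes. SAP 14.3 codes three contrasts, the first beginning "CONTRAST 'CUSA-081 vs Placebo"; the others are CUSA-081 vs alteplase and alteplase vs placebo. Table 14.2.3.1 shows all three ratios with 95% CIs and no p-value.

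On expected success, SAP Section 5 says "The expected placebo response rate is approximately 20" percent. It sizes the non-inferiority test "assuming an equal response rate of 75% in the control arm (alteplase), and the active (CUSA-081) arm" and the placebo comparison on a difference of at least 35 points. These are planning values for the 90-minute endpoint; neither document gives 180-minute rates or a re-occlusion rate.

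SAP Section 12 records that "Since the study has been terminated by the Sponsor prematurely for other reasons, the futility analysis will not be conducted" and that the end-of-study analysis is otherwise kept. It does not list the Cox model among the changes from the protocol.

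**The concern.** Success by 180 minutes happens after randomisation and is what the drugs are meant to change. Subjects who reach it in one arm need not resemble those who reach it in another. If about three quarters of the CUSA-081 arm and one fifth of the placebo arm enter the model, the two groups may differ in how stubborn their occlusions were, and that may relate to how soon they re-occlude. The hazard ratio then mixes any drug effect on re-occlusion with this selection.

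SAP 9.1 uses the same label for the difference in success proportions, which does compare arms as randomised. Table 14.2.3.1 is titled as a Full Analysis Set table, and its hazard-ratio footnote mentions only that treatment is a fixed effect. SAP 7.4 plans no covariate adjustment, and no passage limits how the ratios may be read. They could therefore be quoted as randomised effects on re-occlusion. The two placebo ratios would in addition rest on a handful of events.

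**Working it through.** **Inputs.** Planned arms 473 / 53 / 315 for CUSA-081 / placebo / alteplase (SAP Section 2). Success 75% on both active drugs and about 20% on placebo; at the smallest planned difference CUSA-081 is 20% + 35 = 55% (SAP Section 5). Re-occlusion of 5, 10, 20 or 30% by Day 30 is my assumption.

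**The plan's own figure.** Non-inferiority power with 450 vs 300, 75% in both arms and a 10-point margin: SE = √(0.75×0.25/450 + 0.75×0.25/300) = 0.0323; Φ(0.10/0.0323 − 1.96) = 87.3%, against 87% stated. The success rates and arm sizes used below are thus the ones the plan was built on.

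**Who enters the model.** CUSA-081 473×0.75 ≈ 355; placebo 53×0.20 = 10.6; alteplase 315×0.75 ≈ 236. The fraction selected differs between CUSA-081 and placebo by 75/20 = 3.75-fold, or 55/20 = 2.75-fold.

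**Sparsity of the placebo ratios.** Expected placebo events d₀ = 53×0.20×r; CUSA-081 events d₁ = 473×0.75×r; SE(log HR) ≈ √(1/d₀ + 1/d₁); chance of no placebo event = (1 − 0.20r)^53.

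| Assumed re-occlusion r | d₀ | d₁ | SE | 95% CI around a true HR of 1 | No placebo event |
|---|---|---|---|---|---|
| 5% | 0.5 | 17.7 | 1.39 | 0.07–15.4 | 59% |
| 10% | 1.1 | 35.5 | 0.99 | 0.14–6.9 | 34% |
| 20% | 2.1 | 71.0 | 0.70 | 0.26–3.9 | 11% |
| 30% | 3.2 | 106.4 | 0.57 | 0.33–3.1 | 4% |

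Alteplase vs placebo is about as wide, because d₀ dominates. With no placebo event neither placebo ratio has a finite estimate. If placebo success by 180 minutes were 30% (assumed), there would be 53×0.30 = 15.9 responders and, at 10/20/30% re-occlusion, 1.6/3.2/4.8 events. For contrast, CUSA-081 vs alteplase at r = 20% has 71 and 315×0.75×0.20 = 47 events, so its limits are the HR multiplied and divided by about 1.4.

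The number randomised before termination is not stated. As an illustration, 416 subjects at 9:1:6 give 416/16 = 26 on placebo, and (1 − 0.20r)^26 = 77/59/35/20% at r = 5/10/20/30%.

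**Selection.** All inputs here are assumptions. Let L be ease of opening and U a score for low re-occlusion risk, bivariate normal with correlation ρ. A catheter opens if L exceeds the normal quantile that gives the arm's success rate. The 30-day cumulative hazard is exp(a − bU), the same function in every arm, so there is no drug effect on re-occlusion. Take b = ln 2 (hazard factor 2.0 per SD) and set a so that risk in active-arm responders is 10%. Then HR = ln(1 − r_active)/ln(1 − r_placebo).

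| ρ | −0.5 | −0.3 | 0 | 0.3 | 0.5 | 0.8 |
|---|---|---|---|---|---|---|
| HR vs placebo, 75% vs 20% | 0.73 | 0.83 | 1.00 | 1.23 | 1.41 | 1.78 |

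For CUSA-081 vs alteplase at 75% vs 75% the HR is 1.00 if ρ is the same for both drugs, and 0.82 or 1.22 if one drug has ρ = 0.3 and the other 0.8.

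**The case against.** Little depends on these ratios. Re-occlusion lies outside the testing hierarchy, which covers objectives 1 to 4 (SAP 7.2.1). The objective is to evaluate a rate, and no hypothesis is stated. The restriction is not hidden: SAP 9.3.1 gives it twice, Table 14.2.3.1 shows the number of successes in each arm, and the Figure 14.2.3.1 footnote and the title and footnote of Listing 16.2.6.4 repeat it. The label may simply be the SAP's habitual term for a contrast between arms. A very wide interval also warns the reader by itself, and the placebo Kaplan-Meier curve, which nobody proposes to remove, rests on the same few subjects.

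All of this stands as an argument about weight, and it keeps the point minor. It does not supply the missing statement about randomisation. A wide interval shows imprecision, not selection, and it is no help when there is no placebo event. SAP 7.6 sets a minimum arm size for subgroup comparisons and the subgroup tables define NE; Table 14.2.3.1 has neither. A by-arm curve describes that arm's responders, whereas a ratio labelled as a treatment effect says something about the drugs.

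A reader might infer that the placebo ratios are biased above 1, against the active drugs. The documents do not support that: they do not say whether catheters that are harder to open re-occlude sooner, and the illustration runs to both sides of 1.

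**Conclusion.** The point holds and is minor. The hazard ratios compare subsets defined by an outcome of treatment, and the SAP gives them the label it uses for a randomised comparison. That follows from the design and needs no assumption. The two placebo ratios are the weakest, because the planned success rates differ 2.75- to 3.75-fold; this uses 90-minute planning values for a 180-minute selection.

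The size of any distortion is unknown. The range 0.73 to 1.78 illustrates an assumed model and is not an estimate. Sparsity is firmer: at 20% success about 11 placebo responders are expected whatever the re-occlusion rate, and the event counts of 0.5 to 3.2 rest on the assumed 5% to 30%. Early termination probably makes them smaller, by an amount the documents do not allow one to calculate.

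Two further inferences are not supported. CUSA-081 vs alteplase is also conditional on success, but under the planned equal rates it is neither selected at very different rates nor sparse, so it can stay if labelled properly. And the added Cox model is a gap in the list of changes; it does not affect any confirmatory result.

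**What to change.** 1. Remove the CUSA-081 vs placebo and alteplase vs placebo hazard ratios from SAP 9.3.1, from the 14.3 code (two CONTRAST lines) and from Table 14.2.3.1. Keep the by-arm Kaplan-Meier estimates, Day-30 probabilities and counts, which is what the protocol planned.
2. For any hazard ratio that is kept, including CUSA-081 vs alteplase, replace the sentence in 9.3.1 with: *The hazard ratio with 95% Wald CI is descriptive and conditional on treatment success by 180 minutes; it does not estimate the effect of randomised treatment. It is reported as NE if either arm has no event.* Repeat this as a footnote to Table 14.2.3.1.
3. List the Cox model in SAP Section 12 as an addition to the protocol.

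No replacement analysis is needed. A composite of success without re-occlusion in the whole FAS would answer a question that no objective asks, and initial success would drive it: with 20% re-occlusion in both arms, (0.75 − 0.20)×0.80 = 44 points would come from initial success alone.

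The cost is a few lines of text and code, with no new data. The downside is that the placebo hazard ratios are no longer reported.
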